8.7 Concomitant Interventions (treatments)

Concomitant medication other than psychoactive medication and alcohol are not allowed but will not result in withdrawal.

8.8 Study Drug / Medical Device Accountability

Not applicable

8.9 Return or Destruction of Study Drug / Medical Device

Not applicable

9. STUDY ASSESSMENTS

9.1 Study flow chart(s) / table of study procedures and assessments

See study schedule.

9.2 Assessments of outcomes

9.2.1 Assessment of primary outcome

See primary outcome 5.1.

9.2.2 Assessment of secondary outcomes

See secondary outcome 5.2.

9.2.3 Assessment of other outcomes of interest

See chapter 5.3.

9.2.4 Assessment of safety outcomes

9.2.4.1 *Adverse events*

All (S)AEs occurring after IC confirmation until visit 2 will be fully recorded in the participants eCRF. Description of (S)AE includes time of onset, duration and resolution, assessment of intensity, relationship to study drug, and measures taken. All (S)AEs are post-investigated until resolution.

9.2.4.2 *Laboratory parameters*

No laboratory parameters will be assessed.

9.2.5 Assessments in participants who prematurely stop the study

If participants stopped the study prematurely for whatever reason, a final examination will take place. The examination aims at recording any adverse events.

9.3 Procedures at each visit

9.3.1 Screening visit

During the screening – that is the first part of the first visit- the subinvestigator will again explain the nature of the study, its purpose, the procedures involved, the expected duration, the potential risks and benefits, and any discomfort it may entail. Furthermore, each subject will be informed that participation in the study is completely voluntary and that they can withdraw from the study at any time. Subjects will be informed that authorized individuals, other than the investigators, may analyse the observational data.

Thereafter, participants must read and confirm the informed consent. They will be given a copy of the signed document. The consent form must also be signed and dated by the investigator. It will be kept as part of the participants study records.

Written informed consent will be obtained from all participants without limiting time for signature. Participants who are candidates for enrolment into the study will be evaluated for eligibility during the screening visit (inclusion, exclusion criteria). Screening visit will consist of

- Assessment of medication history

- Vital signs (blood pressure / heart rate) will be taken with the participant having been in a seated position for at least 5 minutes.
- Height / weight (for calculation of BMI)

A pregnancy test will follow in case participants are not sure whether they are pregnant or not. Pregnancy testing will be performed in a urine sample according to instructions of AxaClear®, Axapharm.

The following questionnaires will be used to assess possible psychiatric disorders:

- Sociodemographic questionnaire
- Mental health questionnaire
- Depressive symptoms will be assessed with the self-rating questionnaire MADRS-S (Schmidt1988). This scale consists of 9 items assessing participants' mood, feelings of unease, sleep, appetite, ability to concentrate, initiative, emotional involvement, pessimism and zest for life. Each item is scored between 0 and 3. The total score is calculated by summing the answers of the nine items, ranging between 0 and 27 (higher scores indicate increased impairment).

Screening failures equal to participants not meeting all inclusion criteria or meeting one or more of the exclusion criteria. Excluded participants will be listed on a screening failure log.

9.3.1 Cognitive testing visit 1 and visit 2

There will be a short examination consisting of a THC test, concomitant medication and adverse events. A THC test will be performed in a urine sample according to instructions of THC-Test, MedicTest. The test strip detects THC consumption with a sensitivity of 25 NG/ML. The detection time from last consumption least 3-5 days depending of the consumed amount. (The THC tests will be stored with IMP at the same conditions). Participants eligible for the study will start with the verbal memory task, i.e. learning a list of 15 words (for details see chapter 5.1), followed by an immediate free recall.

Then the participant vapes 0.25mL of the e-Liquid (CBD or perfumed e-Liquid on visit 1 or visit 2 according to the randomization list). After approx. 15 minutes of vaping he/she will perform on the 0-, and 2-back task, followed by some VAS (for details see chapter 5.2). Then, short delay recall of the words will be assessed (for detail see study schedule table).

At the end of each test day participants will be interviewed regarding their actual wellbeing. If there are no complaints / symptoms they can be dismissed. In case of minor health problems, the participant will have to stay in the study centre under medical control until recovery.

The same memory/cognitive test battery will be administered in test days 1 and 2 using parallel versions of the primary and the main secondary outcome measures.

A study compensation of CHF 70 will be paid at the end of visit 2. Screening Failures and Drop-Outs receive a pro rata compensation.

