7. STUDY POPULATION

7.1 Eligibility criteria

Participants fulfilling all of the following inclusion criteria are eligible for the study:

- Healthy
- Normotensive (BP between 90/60mmHg and 140/90mmHg)
- BMI between 18 and 30 kg/m²
- Male or female
- Aged between 18 and 30 years
- Native or fluent German-speaking
- Able and willing to give written informed consent as documented by signature and comply with the requirements of the study protocol
- Willing to donate urine sample to control for pre-Visit CBD/THC consume

The presence of any one of the following exclusion criteria will lead to exclusion of the participant, for example:

- Acute or chronic psychiatric disorder including drug or alcohol abuse
- Women who are pregnant or breast feeding
- Intention to become pregnant during the course of the study
- Smoking (> 5 cigarettes per day)
- Participation in one of our previous studies using the same verbal test in the past 2 years
- Participation in a study with CBD / THC within the 30 days preceding and during the present study
- Known hypersensitivity or allergy to propylene glycol
- Intake of CBD / THC within the 7 days preceding and during the present study in any application form
- Long-term systemic medication or topical steroids to treat an underlying disease within last 3 months
- Inability to follow the procedures of the study, e.g. due to language problems, psychological disorders, dementia, etc. of the participant
- Enrolment of the investigator, his/her family members, employees and other dependent persons

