7.4 Criteria for withdrawal / discontinuation of participants

Participants have the right to withdraw from the study at any time for any reason without being obliged to give reason. There will be a final interview regarding their actual wellbeing after withdrawal for whatever reason. The subinvestigator also has the right to withdraw participants from the study if it is in the best interest of the participant.

The following reasons result in withdrawal:

- Adverse events prohibiting cognitive testing (e.g. nausea, headache)
- Single administration of psychoactive drug within 5 days before visit 2
- Non-Compliance
- Severe protocol violations
- Administrative problems
- Impossibility to vape 0.25mL e-Liquid
- Alcohol intake within 12 hours before visit 2

Withdrawal date and reason (if known) will be listed in the participant enrolment log. Safety data will be analysed for all participants, who received study medication.

A team member, who is not involved in the data sampling procedure, will provide the study leader with replacement e-liquid tanks, in case drop-outs have to be replaced. This way, the randomization order of the randomization list can be maintained. Drop-outs will be replaced until data of 34 participants are completed.

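### Pregnancy is an exclusion, but the only stated test depends on the woman's own doubt at screening, and no check is stated before the visit 2 vape

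*Combined protocol and SAP*

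**What the plan says.** Section 7.1 (Eligibility criteria) lists two relevant exclusions: "Women who are pregnant or breast feeding" and "Intention to become pregnant during the course of the study". Eligibility is asked by telephone and again at visit 1.

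The only pregnancy test is in section 9.3.1 (Screening visit), which is the first part of visit 1: "A pregnancy test will follow in case participants are not sure whether they are pregnant or not". The method is already fixed: "Pregnancy testing will be performed in a urine sample", with a named kit. Anyone who meets an exclusion criterion there is a screening failure.

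The second section numbered 9.3.1 (Cognitive testing visit 1 and visit 2) describes what happens before the vape at both visits: "There will be a short examination consisting of a THC test, concomitant medication and adverse events". Urine is collected from everyone at both visits, but section 7.1 ties it to cannabis control: "Willing to donate urine sample to control for pre-Visit CBD/THC consume". The synopsis gives the same purpose.

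Section 7.4 lists seven reasons for withdrawal. Two are tied to the time before visit 2: alcohol within 12 hours, and "Single administration of psychoactive drug within 5 days before visit 2". Pregnancy is not among the seven.

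**The concern.** The plan sets an exclusion and then verifies it only through what the woman already knows or suspects. Two situations escape:

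- **(a)** a pregnancy at visit 1 that she does not suspect, because only her own doubt triggers the test;
- **(b)** a pregnancy that begins between the visits and is not yet recognised at visit 2, because no check is stated there.

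The handling of cannabis is different: the plan does not rely on self-report but tests everyone's urine at both visits.

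What is at stake is participant safety: a woman the protocol means to exclude could vape CBD (or the control liquid) while pregnant. The primary estimate and the power are not at stake, because drop-outs are replaced until 34 participants complete.

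**Working it through.** The plan gives no figure on this point to reproduce. The check is a comparison of sections, followed by a rough size.

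**1. Which pregnancies does each stated step find?**

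| Step | Where | Finds |
|---|---|---|
| Eligibility questions by telephone and at visit 1 | 7.2, schedule | Known or planned pregnancy |
| Urine test if unsure | 9.3.1, Screening visit | Suspected pregnancy at visit 1 |
| Examination before the vape, visits 1 and 2 | 9.3.1, Cognitive testing | No pregnancy item |
| Inclusion/exclusion item | Schedule | Visit 1 at 00:34; none at visit 2 |
| Withdrawal reasons | 7.4 | Pregnancy not listed; the best-interest clause needs a known pregnancy |

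No row covers (a) or (b).

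**2. How many women are exposed?** The total is 34 (section 11.2), with approximately equal numbers of each sex (section 6.1).

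- Women: 34 × 1/2 = 17.
- Each vapes CBD once, which gives 17 CBD vapes in women.
- Order is balanced on a separate list for each sex (section 6.2.1), so 17/2, or 8 to 9, fall at visit 1 (test only if unsure) and 8 to 9 at visit 2 (no check stated).

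**3. How likely is an exposure?** The documents give no rate of unrecognised pregnancy. Assume p = 0.1% to 1% per woman at her CBD visit.

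- Expected number, 17p: 17 × 0.001 = 0.017, up to 17 × 0.01 = 0.17.
- At least one, 1 − (1 − p)^17: 1 − 0.999^17 = 1.7%, up to 1 − 0.99^17 = 15.7%.

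These figures count CBD vapes only. They include pregnancies too early for a strip to detect, so they overstate what testing could prevent.

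**4. How much of gap (b) would a visit 2 test find?** The documents give no detection window. Assume the strip turns positive 7 to 21 days after conception and that conception is equally likely on any day of the gap. The share found is (gap − lag)/gap, not below 0.

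| Gap (section 6.1) | Lag 7 days | Lag 21 days |
|---|---|---|
| 14 days | 7/14 = 50% | 0% |
| 56 days | 49/56 = 87.5% | 35/56 = 62.5% |

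**5. Does a test fit the schedule without disturbing the primary endpoint?**

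- Start of urine slot to word list: 00:44 − 00:35 = 9 minutes at visit 1; 00:09 − 00:00 = 9 minutes at visit 2.
- Start of urine slot to vape: 00:46 − 00:35 = 11 minutes; 00:11 − 00:00 = 11 minutes.
- Word list to delayed recall: 01:17 − 00:44 = 33 minutes; 00:42 − 00:09 = 33 minutes.

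If the strip is read before the word list, any extra minutes fall before learning and the 33-minute interval is unchanged.

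**The case against.** The strongest case against is proportionality. This is a category A study with one 12.5 mg dose of a retail e-liquid. The plan already excludes known and intended pregnancy, asks about eligibility twice, and tests when in doubt. The risk section (3.7) names sedative effects and no hazard specific to pregnancy. The rate of 0.1% to 1% is assumed, so the 1.7% to 15.7% range only carries a tenfold assumption forward. At the 14-day gap a visit 2 strip may find no pregnancy that began between visits. The drug and alcohol items in section 7.4 may be there because they disturb a memory test, in which case they do not show that a safety check was overlooked.

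Much of this stands, and it keeps the point modest: the risk is low, the range is illustrative, and detection at a short gap is limited. It does not remove the gap. Excluding intended pregnancy does not cover unplanned pregnancy, and best-interest withdrawal works only once a pregnancy is known.

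Section 9.3.1 (Cognitive testing) does speak of eligible participants starting the word task, which could be read as carrying eligibility into visit 2. But it names no pregnancy check, and the schedule has no eligibility item there.

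The checklists mentioned in section 12.1.2 and the consent pages are not visible and might contain a question. The point is therefore limited to the protocol text.

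**Conclusion.** The concern holds. A team that followed the written plan exactly could miss an unsuspected pregnancy at visit 1 and an unrecognised pregnancy that began between visits. The likely number of affected women is well below one. The range in step 3 of the working rests on the assumed rate and on about 17 women, and the detection shares in step 4 rest on the assumed lag. The finding itself rests on neither, since it follows from the text. This is a change the sponsor should make because it is cheap and protects participants. It has no bearing on the analysis or the sample size.

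**What to change.** **Change**

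- In section 9.3.1 and the schedule, run the named urine pregnancy test for every woman on the routine urine at visits 1 and 2, and read it before the word list starts.
- At visit 1, confirm eligibility after the strip is read. The item now stands at 00:34, one minute before urine at 00:35. A positive result is a screening failure.
- At visit 2, list a positive result as a withdrawal reason in section 7.4, with replacement as already planned.
- Widen the stated purpose of the routine urine sample in section 7.1 and the synopsis, and in the participant information if it does not already cover this.
- State that a negative strip does not rule out a very early pregnancy.

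**Cost**

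- Strips: 17 × 2 = 34. If replaced drop-outs and screening failures add an assumed 10% to 20%, 34 × 1.1 = 37.4 (38 strips) to 34 × 1.2 = 40.8 (41 strips).
- Time: the documents give no reading time. At an assumed 0 to 5 extra minutes per test, 34 tests add 0 to 170 minutes (0 to 2.8 hours) over the whole study.
- A short amendment to sections 7.1, 7.4 and 9.3.1, the synopsis and the schedule. If it counts as substantial, section 2.10 requires ethics committee approval first.
- A false positive at visit 2 costs one replacement participant, and staff must be ready to tell a healthy volunteer about an unexpected result.

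No new sample is needed.

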6.2 Methods of minimising bias

6.2.1 Randomisation

By time of visit 1 eligible participants will be randomly allocated to receive either CBD or placebo (perfumed e-liquid) first. To minimise allocation bias, a randomization list will be prepared by a team member of the division of cognitive neuroscience. Block randomization will be used to achieve balance between number of participants starting with CBD and number of participants starting with placebo. A separate list will be used for males and females. The randomization number will be listed in the SD and in the eCRF.

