11. STATISTICAL METHODS

A within-subject design is performed to achieve more Power than a between-subject design by partitioning between-subject variance out of the error variance. No carryover-effects (e.g. practice, fatigue) are expected.

A significance level of $p < 0.05$ (two-sided) will be considered as significant. As there is only one primary outcome measure, no Bonferroni correction will be applied.

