11.2 Determination of Sample Size

We are interested to detect cannabinol effects with at least medium effect sizes. The estimation of $N=34$ is based on a power analysis using dependent t-tests assuming to detect a medium effect size ($d_z = 0.5$) with a power of 80% at $\alpha = 0.05$ (software: G-power 3).

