11.4 Planned Analyses

All analyses will be done in R. Episodic memory performance (memory free recall) and secondary variables of interest will be analyzed by calculating linear mixed models with subject as random effect, experimental condition (Cannabidiol versus placebo) as contrast of interest (fixed effect) as well as the interaction term between experimental condition and covariates (sex, age). In case of significant interactions between covariates and experimental condition, post-hoc tests will be applied to describe the interaction.

Furthermore, to control for possible confounders, possible confounders (words immediate recall, MADRS-S, sociodemographic variables, VAS for mood / arousal / motivation / tiredness / headache / tolerance), subjects' believe about group allocation, will be entered into the model as covariates (each covariate entering the statistical analyses separately).

In case of no significant influence of covariates on dependent variables and in case of no significant interaction of covariate and experimental condition, we will consider to remove covariates out of the statistical model in order to reduce model complexity as far as possible (calculate t-tests in the simplest case).

To illustrate the influence on episodic memory change between experimental conditions, the delta values will be calculated and used dependent variable in an additional analyses. The delta values correspond to the difference in task performance between experimental conditions.

For interim analyses refer to 11.4.3.

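### Parallel test versions are used at the two visits, but the primary model has no visit or version term, so any visit or version difference is left in the error of the CBD contrast

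*Combined protocol and SAP*

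**What the plan says.** - **Versions.** Section 9.3.1, on the cognitive testing visits, states that the battery is "administered in test days 1 and 2 using parallel versions of the primary and the main secondary outcome measures". No section gives the rule that assigns a version to a visit or a participant, or any data on relative difficulty.
- **Randomisation.** Section 6.2.1: "Block randomization will be used to achieve balance between number of participants starting with CBD and number of participants starting with placebo". Sex is handled by stratification: "A separate list will be used for males and females". Version is not mentioned.
- **Model.** Section 11.4 plans "linear mixed models with subject as random effect, experimental condition (Cannabidiol versus placebo) as contrast of interest (fixed effect"), plus the "interaction term between experimental condition and covariates (sex, age"). Further covariates, among them immediate recall of the words, enter one at a time. Covariates without significant influence or interaction may be dropped, down to a plain t-test. Visit, version and sequence appear nowhere. Section 11.4.3 applies the same approach to the n-back.
- **Visit effects.** Section 11 expects no practice or fatigue effects. It does not discuss the difficulty of the versions.
- **Sample size.** Section 11.2: "The estimation of $N=34$ is based on a power analysis using dependent t-tests", for a "medium effect size ($d_z = 0.5$) with a power of 80" per cent. Section 11: "A significance level of $p < 0.05$ (two-sided) will be considered as significant".

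**The concern.** Each participant learns one word list under CBD and another under placebo, at different visits. The paired difference therefore contains the CBD effect plus or minus whatever separates the two lists and the two visits. In a two-period cross-over this nuisance difference is normally removed by a visit (period) term, with a version term as well if versions do not follow visits. The planned model has neither, so the difference is treated as random error.

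What is at stake is mainly precision. The sample size has almost no slack above 80 per cent power, so extra error variance that was not allowed for would take the test below its target. The same structure applies to the n-back, although the plan gives no power statement for that endpoint.

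**Working it through.** **Inputs from the documents.** N = 34 completers, paired t-test, dz = 0.5, two-sided alpha 0.05 (Sections 11 and 11.2). With two observations per person, a random subject effect and a fixed condition effect, the mixed model's test of condition is in essence the paired t-test, so the t-test is used here.

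**Assumption.** Let L be the combined version and visit difference, in units of the SD of the paired difference that remains once it is removed. The documents give neither L nor that SD, so L = 0.2 to 0.8 is an assumed range. If the SD were 2.5 words (also an assumption), this is 0.2 × 2.5 = 0.5 words to 0.8 × 2.5 = 2.0 words out of 15.

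**Step 1: the plan's own figure.** Non-central t with noncentrality 0.5 × √34 = 2.92 and 33 df gives power 0.808. N = 33 gives 0.795. The stated N = 34 is reproduced.

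**Step 2: version tied to visit, 17 participants per product order.** The paired difference is D = effect + L × s + e, where e has SD 1 and s is +1 in one product order and −1 in the other.

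- Bias = L × (17 − 17)/34 = 0.
- The SD that the t-test uses is enlarged by about √(1 + L²), although the true standard error of the mean is still 1/√34. The test is therefore conservative.
- With a visit/version term, L drops out and 32 df remain. Power is 0.807 for every L.

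Simulation (200,000 runs per case):

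| L | √(1 + L²) | Type I error, no term | Power, no term | Power, with term |
|---|---|---|---|---|
| 0 | 1.00 | 0.051 | 0.81 | 0.81 |
| 0.2 | 1.02 | 0.046 | 0.80 | 0.81 |
| 0.4 | 1.08 | 0.035 | 0.76 | 0.81 |
| 0.6 | 1.17 | 0.023 | 0.70 | 0.81 |
| 0.8 | 1.28 | 0.012 | 0.62 | 0.81 |

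With the term, type I error is 0.050 throughout.

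**Step 3: version order drawn at random for each participant.** Here L is the version difference alone. The effective dz is 0.5/√(1 + L²) = 0.490, 0.464, 0.429 and 0.390 for L = 0.2, 0.4, 0.6 and 0.8, giving power 0.79, 0.75, 0.68 and 0.60. Type I error stays near 0.05. The chance imbalance in any one trial has an SD of L/√34 = 0.17 × L. A visit term alone would not remove this; a version term is needed.

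**Step 4: when bias would arise.** With n1 and n2 participants in the two sequences, the bias is L × (n1 − n2)/34. A 19/15 split gives 4/34 = 0.12 × L. If version were tied to product, the bias would be L itself and no analysis could separate the two. These cases are illustrations only.

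**The case against.** A reader might infer that version is unbalanced over product, that the primary contrast is therefore biased, and that the trial loses its stated power. The documents do not support any of these.

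- **Balance.** The plan is silent on version assignment; it does not describe an imbalance. One version per test day is a natural reading of Section 9.3.1, and the blocked product order then balances version over product. Section 7.4 replaces drop-outs so that the list order is kept, and Section 6.2.3 blinds the study team, which makes a link between version and product less likely. Outlier removal without a rule (Section 11.4.1) could unbalance the sequences, but nothing shows that it would do so materially. This part of the objection stands.
- **Stated power.** dz is standardised by the SD of the paired difference. If the 0.5 was meant to include version and visit variance, power is 0.81 as stated, and the extra term would add power to it. This also stands, so the loss in Step 2 is conditional.
- **Size.** The versions are called parallel and practice effects are not expected. At L = 0.2 the loss is about one percentage point.
- **Immediate recall.** It is taken on the same list before vaping and is a planned covariate, so it may absorb part of a list difference in delayed recall. The help is limited: it acts only in the separate model where it is entered, is absent from the t-test, and does not measure the difficulty of n-back versions.
- **The n-back.** It is rule-based letter matching, so word-list reasoning does not carry over automatically. A visit effect remains possible.

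What survives all of this is that, even on the most favourable layout, the planned model leaves a removable source of variance in the error term.

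**Conclusion.** The point holds as one of efficiency and correct test size. As planned, any version or visit difference enters the error of the CBD contrast. With version tied to visit and 17 per order, there is no bias, but the test is conservative: at an assumed difference of 0.4 SD, power is 0.76 and type I error 0.035, against 0.81 and 0.050 with the term. Over 0.2 to 0.8 SD, power without the term runs from 0.80 down to 0.62.

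These figures rest on the assumed range for the difference and on dz = 0.5 excluding that variance; the actual size cannot be determined from the documents. Bias in the primary contrast is a possibility that the missing assignment rule leaves open, and it is not a finding. The change is worth making because it costs almost nothing.

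**What to change.** - **Section 11.4.** Add visit and version as fixed effects to the recall and n-back models, as a single term if the two coincide. Keep them in every model, including those with one added covariate. Exempt them from the significance-based removal of covariates, and take the CBD–placebo contrast from this model instead of a plain paired t-test. In the additional analysis of delta values, include product order (and version order, if crossed), which does the same job.
- **Section 6.2.1.** State the assignment rule for the word lists and the n-back. Either tie each version to a visit, or cross version order with product order within the existing sex-specific lists. Record the version used at each visit.

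**Cost.** One term leaves 32 df (power 0.808 to 0.807). Two terms with balanced crossing leave 31 df (power 0.806). The rest is a sentence or two in each section and, if versions are crossed, one more column in the randomisation list. No extra participants or testing time are needed.
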